ATC	Anatomical Therapeutic Chemical Classification System
AUC	Area under the concentration-time curve
BMI	Body mass index
BSA	Body surface area
CDC	Center for disease control and prevention
CI	Confidence interval
C _{max}	Maximum plasma concentration
CFR	Code of Federal Regulation
CL/F	Apparent clearance
COVID-19	Coronavirus Disease 2019
CSR	Clinical study report
DMC	Data Monitoring Committee
ECG	Electrocardiogram
eCRF	Electronic case report form
eGFR	Estimated glomerular filtration rate
EOS	End of study
EOT	End of treatment
ET	Early termination
ESRD	End-stage renal disease
GCP	Good Clinical Practice
GLP	Good Laboratory Practice
GO	Glycolate oxidase
ICF	Informed consent form
LFT	Liver function test
LLOD	lower limit of detection

LLN	Lower limit of normal
LOD	Limit of detection
MedDRA	Medical dictionary for regulatory activities
O:C	Oxalate: creatinine
PT	Preferred term
SAE	Serious adverse event
SAP	Statistical analysis plan
SC	Subcutaneous
SOC	System Organ Class
SMQ	Standardized MedDRA query
ULN	Upper limit of normal
WHO	World Health Organization
WNL	Within Normal Limits

1. INTRODUCTION

Primary hyperoxaluria type 1 (PH1) is a rare autosomal recessive disease characterized by excessive oxalate production by the liver and consequent hyperoxaluria. PH1 is caused by mutations in the alanine glyoxylate aminotransferase (*AGXT*) gene, which encodes the liver peroxisomal enzyme alanine-glyoxylate aminotransferase (AGT). As a consequence of AGT deficiency, glyoxylate accumulates and is oxidized to oxalate in the hepatocyte and ultimately transported to the kidneys for excretion. Oxalate, in the form of its calcium salt, is excreted almost entirely by the kidney. Due to its insolubility, calcium oxalate can crystallize readily in the urinary tract. In PH1, excess urinary oxalate results in recurrent nephrolithiasis and/or nephrocalcinosis, which can lead to pain, infections, progressive kidney disease including kidney failure, along with reduced quality of life.[\[Cochat and Rumsby 2013\]](#) As renal function declines, elimination of oxalate is further reduced, such that calcium oxalate accumulates in bone, vasculature, skin, retina, heart, and nervous system, resulting in severe end-organ damage.[\[Cochat and Rumsby 2013\]](#) This devastating condition, systemic oxalosis, arises when the estimated glomerular filtration rate (eGFR) has declined to below 30 to 45 mL/min/1.73 m².[\[Cochat and Rumsby 2013\]](#) Without treatment, the disease progresses inexorably, and death from end-stage renal disease (ESRD) and/or complications of oxalosis can occur.[\[Cochat and Rumsby 2013; Harambat 2010; van der Hoeven 2012\]](#)

The ILLUMINATE-C Study (ALN-GO1-005) is a multicenter, single arm study designed to evaluate the efficacy, safety, pharmacokinetics (PK) and pharmacodynamics (PD) of lumasiran in patients with a documented diagnosis of PH1 who have advanced renal disease, as evident by eGFR \leq 45 mL/min/1.73 m² (or serum creatinine above the upper limit of normal (ULN) for age, in patients $<$ 12 months of age). All eligible patients will be administered lumasiran; no control group will be assessed. This statistical analysis plan (SAP) has been developed based on the protocol of the ILLUMINATE-C study (original dated 16 May 2019 and amendment 1 dated 06 May 2020).

The analysis methods described in the protocol may be updated in this SAP. Any change to the data analysis methods described in the protocol, as well as the justification for the change, will be described in the SAP (Section 8) and clinical study report (CSR). Additional exploratory analyses of the data may be conducted when deemed appropriate.

2. STUDY OVERVIEW

2.1. Synopsis of Study Design

The ILLUMINATE-C study (ALN-GO1-005) is a multicenter, multinational, open-label, single arm Phase 3 study designed to evaluate the efficacy, safety, PK and PD of lumasiran in patients with a documented diagnosis of PH1 who have advanced renal disease, as evident by eGFR ≤ 45 ml/min/1.73 m² (or serum creatinine elevated for age, in patients <12 months of age). All eligible patients will be administered open-label lumasiran; no control group will be assessed. This study will consist of 2 periods: a 6-month Primary Analysis Period followed by a long-term (54 months) extension period.

Lumasiran will be administered as a subcutaneous (SC) injection with weight-based dosing, with dose adjustments for interval weight gain, as follows:

Weight	Loading Dose (Day 1, Month 1, Month 2)	Maintenance Dose (Month 3 and Beyond)
<10 kg	6.0 mg/kg monthly for 3 months	3.0 mg/kg monthly
≥ 10 to <20 kg	6.0 mg/kg monthly for 3 months	6.0 mg/kg every 3 months
≥ 20 kg	3.0 mg/kg monthly for 3 months	3.0 mg/kg every 3 months

For patients <6 years of age, the dose will be based on a weight obtained within 7 days prior to dosing. In patients ≥ 6 years of age, body weight collected within 3 months prior to the study drug dose or the predose weight collected on the study visit day or dosing day will be used for dose calculations.

Patients with weight increases crossing the threshold for the next weight-based dosing category (for example, <10 kg to ≥ 10 kg or <20 kg to ≥ 20 kg) will follow the new dosing regimen for the remainder of the study or until the next dosing category threshold is reached (ie, patients will not switch back to the lower-weight dosing schedule if their body weight subsequently decreases).

Patients in maintenance dosing who transition from <10 kg to ≥ 10 kg will continue to receive monthly doses at 3.0 mg/kg until the next quarterly visit (ie Month 3, Month 6, Month 9, etc.) whereby they will follow every 3-months dosing until the end of the study.

This study will include 2 cohorts. Cohort A will include patients who do not yet require dialysis. Cohort B will include patients who are on hemodialysis therapy. Enrollment to both cohorts will occur concurrently. Cohort A patients who experience progression of renal impairment over time and begin to require long-term dialysis therapy will cross-over to Cohort B. Patients in Cohort A who cross-over to Cohort B prior to their Month 6 visit may be replaced. Patients in Cohort B who stop dialysis during the study will continue in Cohort B.

Patients will be screened from Day -120 to Day -1 to determine eligibility. Consented patients meeting all eligibility criteria will receive their first dose of lumasiran on Day 1. From Screening to Day 1, patients will have at least 4 plasma oxalate collections to establish a robust baseline measurement for plasma oxalate.

As specified in the Schedules of Assessments of ALN-GO1-005 protocol, blood samples will be collected in both cohorts for plasma oxalate sample analysis, to establish plasma oxalate profiles

(AUC) in Cohort B, and for PK parameter analysis in both cohorts. In Cohort B, dialysis status and changes in dialysis regimen will also be monitored and documented. During the first 6 months of the study, changes to the dialysis regimen will not be permitted, except when medically necessary.

Safety assessments will include collection of adverse events (AEs), clinical laboratory tests, vital sign assessments, electrocardiograms (ECGs), physical examinations, and concomitant medications.

2.2. Randomization Methodology

Not applicable

2.3. Blinding

ALN-GO1-005 is an open label study, though pharmacodynamic assessment data will not be distributed to the sites until after the patient has completed the Month 6 visit.

2.4. Data Monitoring Committee

An independent Data Monitoring Committee (DMC) will oversee the safety and overall conduct of this study, providing input to the Sponsor. The DMC will operate under the rules of a charter that will be reviewed and approved by the DMC. Details are provided in the DMC Charter.

2.5. Study Procedures

The Schedules of Assessments are described in the study protocol (Tables 1, 2, 3 and 4).

3. ENDPOINTS

3.1. Primary Endpoints

Cohort A

- Percent change in plasma oxalate from baseline to Month 6

Cohort B

- Percent change in pre-dialysis plasma oxalate from baseline to Month 6

3.2. Secondary Endpoints

The following are the secondary endpoints in the Primary Analysis Period:

Primary Analysis Period (Baseline to 6 months)

- Percent change in plasma oxalate AUC between dialysis sessions (Cohort B)
- Absolute change in plasma oxalate
- Change in the following parameters:
 - Urinary oxalate, which is measured by percent and absolute change in 24-hour urinary oxalate excretion corrected for BSA and spot urinary oxalate:creatinine ratio, when available.
 - QoL assessed by the PedsQL Total Score for patients ≥ 2 to < 18 years of age at consent, and as assessed by KDQOL Burden of Kidney Disease and Effect of Kidney Disease on Daily Life subscales, and SF-12 Physical Component Summary and Mental Component Summary, in patients ≥ 18 years at consent
- Plasma PK parameters of lumasiran

The following are the secondary endpoints in the Long-term Extension Period:

Long-term Extension Period (6 months to end of study)

- Percent change in plasma oxalate AUC between dialysis sessions (Cohort B)
- Percent and absolute change in plasma oxalate
- Change in the following parameters:
 - Nephrocalcinosis as assessed by renal ultrasound
 - Frequency and mode of dialysis (Cohort B)
 - Frequency of renal stone events
 - Urinary oxalate, measured by 24-hour urinary oxalate excretion corrected for BSA, and spot urinary oxalate:creatinine ratio
 - Renal function as assessed by eGFR (Cohort A)
 - Measures of systemic oxalosis in the following systems:
 - Cardiac

- Dermatologic
- Skeletal
- Ocular
- QoL (quality of life) assessed by the PedsQL Total Score for patients ≥ 2 to < 18 years of age at consent, and as assessed by KDQOL Burden of Kidney Disease and Effect of Kidney Disease on Daily Life subscales, and SF-12 Physical Component Summary and Mental Component Summary, in patients ≥ 18 years at consent

3.3. Exploratory Endpoints

The following are the exploratory endpoints:

- Growth parameters in patients who are < 6 years of age at consent
- Change in developmental milestones over time in patients < 6 years of age at consent
- Change in QoL as assessed by EQ-5D-Y and PedsQL (individual subscales of the generic and ESRD modules, and ESRD module total score) for patients ≥ 2 to 18 years of age at consent, and as assessed by EQ-5D-5L in patients ≥ 18 years of age at consent
- Change in QoL as assessed by KDQOL Symptoms and Problems of Kidney Disease subscale in patients ≥ 18 years of age at consent
- Change in patient and caregiver resource use (eg, work/school attendance, visits to doctor/hospital)
- Change in patient and caregiver experiences as evaluated by a patient experience questionnaire and a caregiver experience questionnaire
- Frequency of ADA
- Change in urinary and plasma glycolate, where urinary glycolate is measured by urinary glycolate:creatinine ratio

3.4. Safety Endpoint

- Frequency of AEs

4. PATIENT POPULATION

4.1. Patient Definitions

The populations (analysis sets) are defined as follows:

- Safety Analysis Set: All patients who received any amount of lumasiran during study.
- Full Analysis Set: All patients who received any amount of lumasiran and have at least one evaluable plasma oxalate value (pre-dialysis in Cohort B) at baseline and at least one evaluable plasma oxalate value from assessment(s) at Month 3 through Month 6
- PK Analysis Set: All patients who received any amount of lumasiran, have at least 1 postdose blood sample for PK parameters, and have evaluable PK data.

The Safety Analysis Set will be used for safety analyses and the sensitivity analysis of efficacy. The Full Analysis Set will be used to evaluate efficacy endpoints. The PK Analysis Sets will be used to conduct PK analyses.

This study will consist of 2 periods: a 6-month Primary Analysis Period followed by a long-term (54 months) extension period. The Primary Analysis Period starts at the first date/time of lumasiran dose administration and ends at either the date/time of lumasiran dose administration at Month 6 (exception being that Month 6 assessments (eg, plasma oxalate and PK assessments) which occur after the Month 6 dose will be included) or the date of the Month 6 visit (Day 169) for patients who discontinued treatment prematurely. Primary analysis will be conducted using the Primary Analysis Period data collected through 6 months.

The Long-term Extension Period, starts at the date/time of lumasiran dose administration at Month 6 and is through the end of the study. Analysis of the Long-term Extension Period will focus on long-term efficacy and safety effects of lumasiran.

Patients who discontinue from study drug during the 6-month Primary Analysis Period (defined above) will be encouraged to remain on the study and complete assessments (including plasma oxalate but excluding PK assessments) through Month 6. They will also be asked to complete safety follow-up visits, once every 3 months, per the safety follow-up schedule for up to 12 months after the last dose of lumasiran.

Patients who discontinue study drug after Month 6 will be asked to return for their next scheduled visit to complete early termination (ET) assessments and complete safety follow-up visits, once every 3 months, per the safety follow-up schedule for up to 12 months after the last dose of lumasiran.

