Patients with weight increases crossing the threshold for the next weight-based dosing category (<10 kg to \geq 10 kg or <20 kg to \geq 20 kg) will follow the new dosing regimen for the remainder of the study or until the next dosing category threshold is reached (ie, patients will not switch back to the lower-weight dosing schedule if their body weight subsequently decreases).

Patients in maintenance dosing who transition from <10 kg to \geq 10 kg will continue to receive monthly doses at 3.0 mg/kg until the next visit that coincides with Table 4, whereby they will follow every-3-months dosing as per Table 4 until the end of the study.

If a patient does not receive a dose of lumasiran within the specified dosing window, the Investigator should contact the Medical Monitor. After such consultation, the dose may be administered or considered missed and not administered.

If a patient misses multiple consecutive doses, the Investigator, in consultation with the Medical Monitor, will discuss whether the patient will be able to continue the study (see Section 4.3).

Additional details can be found in the Pharmacy Manual. In addition, instructions and procedures related to the administration of lumasiran by a patient or caregiver will be provided in the Patient/Caregiver Storage and Administration Instructions.

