7.6. Safety Analyses

Primary safety analysis is a descriptive summary of frequency of AEs using the Safety Analysis Set. Other safety parameters will include vital signs, ECGs, clinical laboratory assessments and physical exams.

Safety analysis will be conducted for the Primary Analysis Period and extension period.

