7.6.1. Adverse Events

The primary safety parameter is treatment emergent AEs. A treatment emergent AE will be defined as an AE that occurs or worsens on/after the first dose date/time of lumasiran through 84 days after the last dose. In addition, any AE that worsened in intensity or was subsequently considered related to lumasiran will be considered treatment emergent.

AEs will be classified using the Medical Dictionary for Regulatory Activities (MedDRA Version 21.1 or later) and displayed in tables using System Organ Class (SOC) and Preferred Terms (PT). All treatment emergent AEs hereafter will be referred to as AEs in this document.

An overview table of AEs will be generated. The overview table will include the number and percentage of patients in categories such as, but not limited to:

- At least 1 AE
 - At least 1 drug related AE
- At least 1 severe AE

- At least 1 drug related severe AE
- At least 1 Serious Adverse Event (SAE)
 - At least 1 drug related SAE
- At least 1 AE leading to treatment discontinuation
 - At least 1 drug related AE leading to treatment discontinuation
- At least 1 AE leading to study withdrawal
 - At least 1 drug related AE leading to study withdrawal
- At least 1 AE leading to treatment interruption
 - At least 1 drug related AE leading to treatment interruption
- Death

Tabulations by System Organ Class (SOC) and Preferred Term (PT) displaying the number of patients (percentage) and total events will be produced for the following tables:

- All AEs
- Severe AEs
- AEs by Maximum Severity
- AEs related to treatment
- AEs related to treatment by Maximum Severity
- All SAEs
- SAEs related to treatment
- AEs leading to treatment discontinuation
- AEs leading to treatment interruption
- AEs leading to study withdrawal

Tabulations by PT in decreasing order of frequency will be generated for the following tables:

- All AEs
- All SAEs
- AEs related to treatment
- SAEs related to treatment

There will also be an All AE table generated displaying rates of AEs adjusted for exposure-time.

Patients who report multiple occurrences of the same AE (preferred term) will be classified according to the most severe occurrence or most related.

Separate listings will be provided for deaths, SAEs, and AEs leading to discontinuation of study drug, withdrawal of study drug and/or dose interruption. By-patient AE listings will be provided.

Additional summaries will also be generated:

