7.6.2. Dosing and Extent of Exposure

Summaries of exposure will include the following characteristics such as, but not limited to: the total number of doses received per patient, mean number of doses per subject, cumulative number of doses received, duration of drug exposure (months), cumulative drug exposure time (months), the total dose administered (mg) and total volume administered (mL).

Definition of drug exposure (days) will be defined as the minimum of [Exposure time= (date of last exposure – date of first dose +1)] where date of last exposure will represent either the date of the last dose administered dose +84, analysis cut-off date or end of study date, whichever occurs first. The exposure during the Primary Analysis Period will be right censored; that is, the date of the last exposure will not be later than the first date of dosing in the Extension Period.

Dose interruptions and compliance are not taken into account.

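### In early discontinuers, some treatment-emergent AEs after Day 169 fall in neither study period although exposure is still counted; the period boundary is also undefined when a Month 6 dose is skipped

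*SAP*

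**What the plan says.** SAP 4.1 gives the Primary Analysis Period two possible ends. It "ends at either the date/time of lumasiran dose administration at Month 6", "or the date of the Month 6 visit (Day 169) for patients who discontinued treatment prematurely". The next period has one start: "The Long-term Extension Period, starts at the date/time of lumasiran dose administration at Month 6 and is through the end of the study". The same section has early discontinuers followed for safety every 3 months for up to 12 months after the last dose, so their AEs go on being collected.

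SAP 5.2 fills each period's tables and figures with the data collected in the period as SAP 4.1 defines it. SAP 7.6 states: "Safety analysis will be conducted for the Primary Analysis Period and extension period".

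SAP 7.6.1 counts an AE as treatment emergent if it occurs or worsens "on/after the first dose date/time of lumasiran through 84 days after the last dose". A further clause, with no time limit, adds AEs that worsened or were later judged related. The section also plans an all-AE table adjusted for exposure time.

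SAP 7.6.2 ends exposure at last dose + 84 days, the analysis cut-off or the end of study, whichever is first. For the primary period it adds one censoring rule: "the date of the last exposure will not be later than the first date of dosing in the Extension Period".

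The protocol lets a continuing patient go without a scheduled dose. Section 5.2.2 says that outside the window "the dose may be administered or considered missed and not administered", and 5.2.3 and Table 11 allow a dose to be held.

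**The concern.** The four rules do not share an end point. For an early discontinuer, the period rule stops on Day 169, and the treatment-emergence and exposure rules stop at last dose + 84 days. If the second date is later, AEs in between count as treatment emergent but belong to no period. The only stated censoring of primary-period exposure is a first extension dose, which this patient never has, so exposure is not cut at Day 169. The exposure-adjusted rate then has a denominator longer than the time over which events are counted, and is too low for that patient.

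The second issue is separate. A patient still in the study whose Month 6 dose is skipped, with dosing resumed later, has not discontinued and has no Month 6 dose. Neither end condition is met and the extension has no start.

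AE frequency is the only safety endpoint in SAP 3.4. With 20 patients, one patient is 1/20 = 5 percentage points of an overall incidence, so the counting rule should leave no doubt.

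**Working it through.** **Inputs.** One month is 28 days (protocol Table 1 notes). Maintenance dosing before Month 6 is at Months 3, 4 and 5 under 10 kg, and at Month 3 only from 10 kg up (protocol Table 10). The visit window is ±4 days at Months 3 to 5, widened to ±14 days under COVID-19 (protocol Table 1). The 84-day rules are in SAP 7.6.1 and 7.6.2.

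**The plan's own figure.** Study day of Month m = 28m + 1, so Month 6 = 28 × 6 + 1 = 169. This reproduces the SAP's Day 169.

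**Formulas.** With last dose on Day L:
- end of the treatment-emergent window and of exposure = L + 84 (exposure from Day 1 is therefore L + 84 days)
- gap = max(0, L + 84 − 169)
- rate ratio = 169 / (L + 84) when the gap is above 0, assuming a constant AE rate

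| Last dose | L | L + 84 | Gap (days) | Gap / exposure | Rate ratio |
|---|---|---|---|---|---|
| Month 2, any weight | 57 | 141 | 0 | 0% | 1.000 |
| Month 3, any weight, on schedule | 85 | 169 | 0 | 0% | 1.000 |
| Month 3, 4 days late | 89 | 173 | 4 | 2.3% | 0.977 |
| Month 3, 14 days late | 99 | 183 | 14 | 7.7% | 0.923 |
| Month 4, under 10 kg | 113 | 197 | 28 | 14.2% | 0.858 |
| Month 5, under 10 kg | 141 | 225 | 56 | 24.9% | 0.751 |

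A Month 2 dose given 14 days late still ends at 71 + 84 = Day 155, so it leaves no gap. With Months 4 and 5 dosed 14 days late, the gaps are 127 + 84 − 169 = 42 and 155 + 84 − 169 = 70 days. If the boundary is the actual Month 6 visit date (Day 162 to 176 under the ±7 window), the on-schedule gaps are 7 to 0 days (Month 3), 35 to 21 (Month 4) and 63 to 49 (Month 5).

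**Study level.** The documents do not give the number of discontinuers. Assume k of 20 stop after Month 5 and the others contribute 169 days each. Unmatched share = 56k / [169(20 − k) + 225k]:
- k = 1: 56 / 3436 = 1.6%
- k = 2: 112 / 3492 = 3.2%
- k = 4: 224 / 3604 = 6.2%

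**Relatedness clause.** An AE later judged related is treatment emergent whenever it occurs. In an early discontinuer of any weight, such an AE after Day 169 falls in neither period. No exposure beyond last dose + 84 days is counted for it, so the problem there is a missing count, not an inflated denominator.

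**No Month 6 dose.** If the dose is given late, the primary period ends late and the extension starts late. If dosing stops for good, the Day 169 branch applies. Only a dose skipped outright with later dosing has no rule. In that case the primary period never closes, so it keeps both the AEs and the exposure.

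**The case against.** The best defence is that SAP 5.2 limits every period summary to data in the period, so it could limit exposure as well as AEs. SAP 7.6.2 does speak of exposure during the primary period as censored. On that reading numerator and denominator both stop on Day 169 and no rate is biased. The reading is possible, but SAP 7.6.2 states a different cut, and even if it is accepted the AEs after Day 169 remain untabulated.

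A second defence is that nothing is hidden. SAP 7.6 does not say that period tables are the only ones. SAP 5.8 promises that all data will be summarised in the primary-period and final reports. SAP 7.8.3 plans a summary of any AE and any SAE by pandemic phase, not by study period. Deaths, SAEs and AEs leading to discontinuation have their own listings, and all CRF data are listed. This stands in part: the events will be visible patient by patient. But SAP 5.8 names no AE table and sits awkwardly with SAP 5.2 and 7.6, and neither listings nor the pandemic-phase summary supply the main incidence and rate tables.

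The defence is right on several stronger readings that the documents do not support:
- A reader might infer that a held or missed Month 6 dose also loses events. It does not; it leaves their period undefined.
- A reader might infer that these patients mostly stopped for safety. Protocol 4.3.1 lists several non-safety reasons and gives no frequencies.
- A reader might infer that extension efficacy summaries are lost. The extension analysis text is redacted, so this cannot be checked.

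**Conclusion.** The inconsistency is real on the literal text and worth correcting, but it is narrow. Under the 84-day rule it is material only for patients under 10 kg whose last dose was at Month 4 or 5. For a patient of 10 kg or more the Month 3 dose plus 84 days lands exactly on Day 169, so only late dosing opens a gap.

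The 25% figure is one patient's exposure, and it would be wrong to read it as the bias in the study's AE rate; the study-level share is the 1.6% to 6.2% shown above. Those figures rest on an assumed 1 to 4 Month 5 discontinuers among 20 patients. The gap itself assumes that the patient stays in follow-up to last dose + 84 days and that the analysis cut-off falls no earlier; otherwise it is shorter.

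The skipped-dose case is a question of allocation between periods and should be settled by the same rule.

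**What to change.** 1. In SAP 4.1, give every treated patient one boundary: the Month 6 dose or, where none is given, the Month 6 visit date (Day 169 if there is no visit).
2. Tabulate discontinuers' treatment-emergent AEs after that boundary through last dose + 84 days, or end of study if earlier. Either a separate on-study follow-up column or one cumulative AE, SAE and death table from first dose to last dose + 84 days would do. State there where a later event that qualifies only through relatedness is shown.
3. In SAP 7.6.2, cut exposure at the same boundary as the AE counts it is paired with. A cumulative table would use exposure to last dose + 84 days; for a last dose at Month 5 that is 225 days of AE time over 225 days of exposure, instead of 169 over 225.
4. Reconcile the all-data statements in SAP 5.8 with the period rules in SAP 5.2 and 7.6.

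There is no need to extend the tables to the full 12 months of follow-up, which would go beyond the SAP's own 84-day rule. The cost is two sentences and one extra table, with no change to trial conduct. AE counts or rates may rise slightly.
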